9.4.3 ANALYSIS OF THE SECONDARY ENDPOINT(S)

Secondary outcomes will be presented as descriptives tabulated by whether treated, treatment group and time, showing medians and ranges. No inferential analyses will be conducted, in order to minimize the multiple testing problem.

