	 vitro data (160 J/cm² to 480 J/cm²), we will conduct a dose-ranging, randomized, parallel group, split-face, single-blind, mock-controlled Phase II study to evaluate the efficacy of LED-RL phototherapy in preventing or limiting skin fibrosis in a mini-facelift surgical wound model. Primary Objective: To evaluate the clinical efficacy of LED-RL phototherapy in the prevention of skin fibrosis in subjects undergoing elective mini-facelift surgery Secondary Objectives: To evaluate the histological, ultrastructural, and molecular changes that occur in vivo as a result of LED-RL phototherapy To detect clinically meaningful changes in scar characteristics after LED-RL phototherapy To continue to assess the safety of LED-RL phototherapy on human skin
Endpoints:	 Primary Outcome Measure: Difference in quantitative scar pliability between the treated and control incision sites Secondary Outcome Measures: Difference in objective measurements of key scar characteristics (collagen and water concentration, wrinkles, texture, diameter, area, volume of elevation, pores, pigmentation, vascularity) between the treated and control incision sites Difference in the Patient and Observer Scar Assessment Scale (POSAS) scores between the treated and control incision sites Difference in the photograph-based Visual Analogue Scale (VAS) scores between the treated and control incision sites Histological and molecular analyses of treated and control skin specimens Incidence of adverse events
Study Population:	A total of 30 subjects will be enrolled. Individuals of any sex, race/ethnicity, and age who are suitable candidates for mini-facelift surgery and who do not meet exclusion criteria will be eligible for this study.
Phase:	2
Description of Sites/Facilities Enrolling Participants:	Subjects will be enrolled at a single site, SUNY Downstate Medical Center. The study is not intended to include sites outside of the US.

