	Difference in the photograph-based Visual Analogue Scale (VAS) scores between the treated and control incision sites An independent panel of two blinded dermatologists will evaluate standardized split- face scar photographs, using a validated VAS scoring and ranking system. ^{53,62,63} Each scar dimension is rated on a 10 cm VAS such that	The VAS has demonstrated high observer reliability and internal consistency in expert panel evaluations. ^{53,63} The VAS has been used in various scar trials ⁵³ and Duncan et al. showed that the VAS scar scoring and scar ranking methods are consistent, reliable, valid, and feasible for assessing linear scars. ⁶²

OBJECTIVES	ENDPOINTS	JUSTIFICATION FOR ENDPOINTS
	higher numerical scores correlated with more	
	severe scars.	
	Difference in objective measurements of key	OCT has been used to non-invasively
	scar characteristics between the treated and	evaluate skin fibrosis at high resolution
	control incision sites	without discernible effect on tissue. ⁶⁵ This
		imaging technique is highly suited to
	A diverse set of novel, non-invasive skin	fibrosis assessment and may represent a
	analysis tools will be used to objectively	diagnostic alternative to punch biopsies. ⁶⁶
	measure key scar characteristics: collagen and	
	water concentration, wrinkles, texture,	Three-dimensional skin imaging analysis
	diameter, area, volume of elevation, pores,	provides quantitative measurements of
	pigmentation, and vascularity. The VivoSight	various scar tissue indicators such as
	uses multi-beam OCT technology to provide	pigmentation, vascularity, texture, and
	high-resolution cross-sectional images and	volume of depressions and elevations.
	measure scar depth, collagen density, and	Because it is an objective analysis tool, it
	surface roughness. ⁶⁴ The Dermo is a	provides quantitative evidence of
	spectroscopy probe that measures collagen and	therapeutic results, avoiding the influence
	water concentration in the dermis. The Antera	of subjective evaluation that most scar
	3D camera and Cherry3 camera use multi-	assessments are based on. ^{67–69} It has been
	directional illumination to reconstruct three-	used to assess therapeutic efficacy of
	dimensional images of the skin surface for	various interventions on keloids and burn
	instant topographic and colorimetric analyses.	scars.
	These objective efficacy assessments will be	
	done prior to treatment initiation and at	
	follow-up visits.	

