4.2 SCIENTIFIC RATIONALE FOR STUDY DESIGN

The methodology of a dose-ranging, randomized, parallel group, split-face, single-blind, mock-controlled study offers several advantages.

A dose-ranging study design is implemented as the safety of LED-RL phototherapy in a surgical wound model may differ from the safety in normal skin. For example, higher fluences determined to be safe in normal skin may potentially cause problems in post-surgical/scarred skin, such as dehiscence. Thus, the MTD established in our Phase I studies serves as the upper limit of treatment dose in this study.

The split-face study design allows each subject to serve as his or her own control, allowing for a within-subject comparison of clinical efficacy between the treated side and mock-treated side. That is, any observed improvements in scar characteristics can be attributed to the treatment. The split-face design also eliminates the need to consider inter-individual differences in wound healing as a confounding factor when comparing different treatment arms. It is important to note that in the prospective evaluation of scar reduction therapy, it is assumed that if left untreated, the wounds on the treated side and untreated side would heal with identical scars. Since wound healing and scar

formation are influenced by many variables, the selection of a self-controlled study design is favored to allow detection of true treatment effects.

There are no known problems associated with the control (sham irradiation), since the mock device is designed to simulate the treatment device without actually producing light.

The mini-facelift with periauricular incisions is an ideal model for studying wound healing and skin fibrosis because: patients are motivated to have the best wound healing outcomes and aesthetic results (i.e., minimal or imperceptible scarring), hence will likely be compliant with therapy and have a low attrition rate; patients are usually healthy in order to be suitable candidates for the surgery; and the periauricular skin is at risk of pathological scar development, yet has low skin tension and robust blood circulation to allow for optimal wound healing.

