9 STATISTICAL CONSIDERATIONS

9.1 STATISTICAL HYPOTHESES

- Hypothesis for Primary Efficacy Endpoint: There is a statistically significant difference in scar pliability between a LED-RL-treated incision and a mock-treated incision.
 - Skin elasticity and induration (an index of scar pliability) are measured pre-treatment at the first treatment session and post-treatment on follow-up visits at POD 30, 90, and 180.
- Hypothesis for Secondary Efficacy Endpoint(s): LED-RL phototherapy treatment results in a statistically significant improvement in POSAS score and VAS score compared to mock treatment.

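### Section 9.1 hypothesises significance for POSAS and VAS while 9.4.3 bars testing, and 9.4.3 gives no within-subject summary for three secondary endpoints defined as treated-versus-control differences

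*Combined protocol and SAP*

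**What the plan says.** **Hypothesis.** Section 9.1 sets as the secondary hypothesis that "LED-RL phototherapy treatment results in a statistically significant improvement in POSAS score and VAS score compared to mock".

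**Analysis.** Section 9.4.3 plans for these outcomes "descriptives tabulated by whether treated, treatment group and time, showing medians and ranges". It then rules out any testing: "No inferential analyses will be conducted, in order to minimize the multiple testing problem".

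**Endpoint definitions.** The synopsis lists five secondary outcome measures. Three are differences between the two sides of the face:
- For POSAS, the synopsis has "Difference in the Patient and Observer Scar Assessment Scale (POSAS) scores between the treated and control incision sites".
- For VAS, Section 3 (and likewise the synopsis) has "Difference in the photograph-based Visual Analogue Scale (VAS) scores between the treated and control incision sites".
- For the objective measures, the synopsis has "Difference in objective measurements of key scar characteristics (collagen and water concentration" and eight further characteristics), again comparing the two sides.

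The other two, histology/molecular analyses and adverse events, are not defined as differences and are outside this point.

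**Design rationale.** Section 4.2 justifies the split-face design as "allowing for a within-subject comparison of clinical efficacy between the treated side and mock-treated side".

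**The concern.** There are two separate problems.

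1. A hypothesis of statistical significance needs a test, and the analysis section forbids one. As written, the 9.1 statement on POSAS and VAS can be neither supported nor rejected. It could also be cited later to justify unplanned tests, which is the multiplicity problem that 9.4.3 sets out to avoid.

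2. The planned table is not a summary of the endpoints as defined. A difference of side means equals the mean of the paired differences, but medians do not have that property, and two side ranges say nothing about the range of the differences. A reader would see neither the typical within-subject difference nor how consistently subjects did better on the treated side. That comparison is the reason given for treating one side and mocking the other. The bar on inference does not explain the gap, because a median paired difference is itself descriptive.

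**Working it through.** **Step 1. Is a test or a paired summary planned elsewhere?**

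| Section | Content | Test for POSAS or VAS? | Paired summary of the three endpoints? |
|---|---|---|---|
| 9.4.2 | Mixed models for elasticity and induration | No | No |
| 9.4.3 | Medians and ranges by side, dose group and time | Excluded | No |
| 9.4.7 | Demographic regression on pliability | No | No |
| 9.4.8 | Listing of individual values | No | No |
| 9.4.9 | Not applicable | No | No |

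Sections 3 and 8.1 mention VAS ranking, but no section says how ranks would be summarised. The plan states no figure for any secondary endpoint, so there is none to reproduce; the power statement in Section 9.2 concerns pliability only.

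**Step 2. A concrete case.** All scores here are assumed, within the POSAS total range of 6 to 60 in Section 8.1, for one dose group of n = 10.

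- Mock side: 10, 12, ..., 28. Median (18 + 20)/2 = 19, range 10 to 28.
- LED side: 7, 9, ..., 25. Median (15 + 17)/2 = 16, range 7 to 25.
- Difference of side medians: 16 - 19 = -3.

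Two pairings give exactly this table:

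- *In order.* Every subject has difference -3; the spread (maximum minus minimum) is 0 and nobody is worse on LED.
- *LED in the order 7, 9, 11, 13, 15, 21, 23, 25, 17, 19.* The differences are -3 five times, +1 three times and -9 twice. The median is -3, the spread is 1 - (-9) = 10, and 3 of 10 are worse on LED. Both sides are equally spaced, so r = 1 - 6 x sum(d^2)/[n(n^2 - 1)] with d the rank shift: r = 1 - 6 x (4 + 4 + 4 + 9 + 9)/990 = 1 - 180/990 = 0.82.

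**Step 3. All pairings.** Every one of the 10! = 3,628,800 pairings has the same side medians and ranges. Section 4.2 says "it is assumed that if left untreated, the wounds on the treated side and untreated side would heal with identical scars", so high between-side correlation is the relevant case.

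| Correlation | Pairings | Median paired difference | Exactly -3 | Spread | Subjects worse on LED |
|---|---|---|---|---|---|
| r >= 0.7 | 48,539 | -5 to -1 | 27,049 (56%) | 0 to 18 | 0 to 5 |
| r >= 0.9 | 1,465 | -5 to -1 | 1,293 (88%) | 0 to 10 | 0 to 2 |

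- At r >= 0.7, 1 to 3 subjects are worse in (9,082 + 22,499 + 14,062)/48,539 = 94% of pairings.
- At r >= 0.9, the median lies between -4 and -2 in 1,453 of 1,465 pairings (99%).
- At r >= 0.5 there are 261,323 pairings and the median runs from -7 to +1. It is positive in 104 of them. The highest r at which a positive median occurs is 0.64, so there are none at r >= 0.7.

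These counts show what the table leaves open. They are not probabilities.

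**Step 4. Model-based check.** Assume bivariate normal scores with equal SDs, n = 10, and 200,000 samples per r. The absolute gap between the difference of side medians and the median paired difference is:

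| r | Typical (median) gap | 90th percentile |
|---|---|---|
| 0.5 | 0.20 SD | 0.52 SD |
| 0.7 | 0.18 SD | 0.47 SD |
| 0.9 | 0.13 SD | 0.34 SD |

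For spread, SD(difference) = SD x sqrt[2(1 - r)]. That is sqrt(0.6) = 0.77 SD at r = 0.7 and sqrt(0.2) = 0.45 SD at r = 0.9. It depends on r, which the planned table does not show.

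**The case against.** The strongest reply is that both problems are small. Section 9.4.3 is the operative section: it is unambiguous and gives a sound reason, so an analyst would run no secondary test and no error rate, sample size or primary result changes. The table shows both sides within each dose and visit, which allows an informal comparison. The primary mixed model includes subject as a random factor, so the split-face design is used where inference is made. Paired differences could be computed from the 9.4.8 listings. If the two sides are very highly correlated, the difference of side medians is close to the median paired difference, and the model-based check shows no systematic bias in it.

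Most of this stands, and it limits the size of the concern. It does not remove it. The two sections still contradict each other. The listings leave the handling of the two VAS raters and of the pre-treatment difference to be chosen after the data are seen. The close agreement at high correlation concerns location only: even at r >= 0.9, between 0 and 2 of 10 subjects may do worse and the spread may be anything up to 10 points.

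It is also fair that extra rows lengthen the table and may invite informal comparisons, and that a median and range do not report how many subjects did worse. These points bear on how the fix is laid out, not on whether it is needed.

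**Conclusion.** The concern holds on both counts. The contradiction between 9.1 and 9.4.3 is a matter of text and rests on no assumption. That side-specific medians and ranges do not determine the within-subject difference is a mathematical fact. How much it matters depends on assumed scores and correlations, since the documents give none. On those assumptions the loss is mainly in spread and consistency across subjects, less in the typical difference, and a reversed sign is rare. Descriptive-only analysis of secondary endpoints is a legitimate choice and is not criticised here. The primary analysis is unaffected. The change should be made because the planned summary does not deliver three endpoints as the protocol defines them, and correcting it is cheap.

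**What to change.** **Section 9.1.** Replace the secondary hypothesis with a descriptive aim: to describe the within-subject LED-minus-mock difference in POSAS and VAS scores.

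**Section 9.4.3.** Compute LED minus mock for each subject at each visit for the POSAS observer score, the POSAS patient score, VAS and each objective scar measure. For VAS, average the two raters before subtracting; the plan is silent on this, so another rule would serve if fixed in advance. Add the median and range of these differences by dose group and visit to the planned table, with the pre-treatment difference as its own row where a baseline is collected. Keep the no-inference rule and add no confidence intervals.

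Two optional additions: the number of subjects who did worse on the LED side, and a sentence saying how VAS ranks will be summarised or that they will not be.

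**Cost.** Two wording edits and a few lines of programming on data already collected, with no new visits, measurements or tests. The table grows: the synopsis names ten objective characteristics, so with three doses and four time points these alone add up to 10 x 3 x 4 = 120 median-and-range entries. An appendix table would hold them.

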9.4.4 SAFETY ANALYSES

AEs, SAEs, and UPs will be recorded and reported as described in the protocol. The information documented about each event or problem includes onset, duration, severity, relationship to the study intervention, and outcome. Summary statistics of safety data will be presented as number of subjects who experienced AEs in each treatment group and a breakdown of the event types. AEs will be coded according to the terminology in the Medical Dictionary for Regulatory Activities (MeDRA). AEs leading to premature discontinuation from the study and serious treatment-emergent AEs will also be presented.

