2.3 RISK/BENEFIT ASSESSMENT

2.3.1 KNOWN POTENTIAL RISKS

We do not anticipate significant social, financial, legal or other risks to subjects from the proposed study, and the likelihood and seriousness of these risks occurring is low. Possible psychological risks include study boredom during longer treatment sessions and dissatisfaction or disappointment with the cosmetic outcomes of the mini-facelift surgery and/or post-treated incisions. Subjects may

experience financial loss (e.g., transportation costs) and loss of time due to study participation. Although there is minimal legal risk and all appropriate safeguards are in place to prevent dissemination of protected health information (PHI), subjects may experience breach of data.

Physical risks of the proposed mini-facelift surgery are as follows: bleeding, hematoma formation (bruising), infection, facial nerve injury with weakness, change in skin sensation, cutaneous or fat necrosis, seromas (fluid collection), scarring, poor wound healing, temporary or permanent alopecia (hair loss) at incisions, swelling, pain, skin sensitivity, skin contour irregularities, skin discoloration, facial asymmetry, irritation from sutures, wound separation, and discomfort from injection of local anesthesia. Any of the above risks may be immediate or long-term complications. As mentioned above, the subject may feel disappointed or upset by unsatisfactory results or surgical complications. The selection of mini-facelift surgery to serve as the surgical wound/scar model for this study is explained in *Section 2.3.3: Assessment of Potential Risks and Benefits*.

Risks of the local anesthesia used during the mini-facelift surgery include: allergic reaction, bleeding, discomfort from the injection, injury from the needle used to inject the anesthesia, paresthesia (abnormal skin sensation such as burning, numbness, and tingling), and toxicity from excessive dose of anesthesia given.

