Physical risks of the proposed LED-RL phototherapy include potential toxicity and lack of efficacy. There is low risk of infection as we will not treat non-intact skin (since presence of open wound(s) at the treatment site is an exclusion criterion) and all LED-RL phototherapy devices will be cleaned with disinfectant before and after each treatment session. Common expected post-treatment effects include mild erythema (redness), warmth, and swelling that is transient (i.e., lasts less than 24 hours). Subjects may have tenderness or swelling at the treatment site. Since darker skin pigment absorbs more light energy in the epidermis, it is possible that subjects with darker skin types may experience a greater sensation of epidermal warmth, textural changes, or dyspigmentation. Due to the split-face study design (i.e., only one surgical incision receives LED-RL phototherapy), there is a possibility of uneven cosmetic results of the scar appearances at the conclusion of the study. That is, the scar on one side of the face may look better, worse, or the same as the scar on the other side.

Potential serious adverse events including, but not limited to, second-degree or higher skin burning, blistering, persistent swelling, persistent pain, ulceration, change in sensation, mucle weakness, or worsening of surgical scar will be monitored and the trial will be halted early if necessary. While we have tested the effects of LED-RL on fibroblasts, it is not known whether LED-RL alters the function of other cell types *in vivo*. At the doses studied, there may be inhibitory effects on other cells found in the epidermis and dermis such as keratinocytes, melanocytes, endothelial cells, neurons and immune cells. Due to the location of LED-RL phototherapy on the face, there is a theoretical risk of neurological side effects such as headaches, malaise, fatigue, and change in hearing.

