We do not anticipate any physical risks of the mock irradiation since it does not generate light and there were no adverse events associated with the mock treatment device in the Phase I studies. However, due to the split-face study design, subjects may have uneven cosmetic results between the two periauricular incision sites. The scar on one side of the face may appear better, worse, or the same as the scar on the contralateral side, depending on the effects of the study intervention. A proposed component of this study is optional skin biopsies for histological examination. Though a skin biopsy is a generally safe procedure, potential risks include bleeding, bruising, scarring, pain, skin sensitivity, and infection.

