6.1.2 DOSING AND ADMINISTRATION

Randomization:

A computer-based randomization algorithm will be used to assign subjects to three different treatment groups to receive LED-RL at the following doses: 160 J/cm², 320 J/cm², or 480 J/cm². The treatment side (right face versus left face) will also be randomized using the same algorithm. The same dose will be maintained throughout all treatment sessions for each individual subject, with no dose escalation. Refer to *Section 6.3: Measures to Minimize Bias* for a detailed description of the randomization protocol.

Treatment Protocol:

The subject will be inside a private clinic examination room. The subject's periauricular skin on both sides of the face will be cleaned with alcohol pads. A surgical marking pen will be used to outline the treatment area at the start and completion of every treatment. The Omnilux new-U device and mock therapy device will be aimed at the periauricular skin and positioned in close contact with the skin (maximum of 1 cm from the skin surface), held in place by a hair net throughout the duration of the treatment. LED-RL phototherapy and mock therapy are administered simultaneously. Subjects will be allowed to receive the treatment sitting up or laying down, per personal preference for a comfortable position.

Duration of the treatment administration for each group is as follows:

- Group 1: LED-RL 160 J/cm² and mock therapy 30 minutes
- Group 2: LED-RL 320 J/cm² and mock therapy 60 minutes
- Group 3: LED-RL 480 J/cm² and mock therapy 90 minutes

[name] (research coordinator) will perform the phototherapy, observe the treatment session, and assess for any safety issues that may arise. Any adverse events reported by the subject or observed by the investigator will be recorded. Common expected post-treatment effects include mild erythema, warmth, and swelling, which are expected to resolve within 24 hours.

Subjects will receive LED-RL phototherapy and mock therapy sessions in-office three times weekly, starting at approximately 1 week post-surgery, for a total of nine treatment sessions. The duration of treatment administration is controlled by the investigator (i.e., the investigator will take responsibility for timing the treatment and determining when the devices are turned off to end treatment).

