6.3 MEASURES TO MINIMIZE BIAS: RANDOMIZATION AND BLINDING

Treatment Dose Randomization

A block randomization scheme will be used for balanced allocation of subjects to study arms, such that 10 subjects are assigned to each treatment group. All subjects will be randomized as they are enrolled

(i.e., sequentially in blocks of three). Study enrollment concludes when a total of 30 subjects have been randomized.

For the first subject who enrolls, Arabic numeral "1", "2", or "3" will be generated at random using a computer-based randomization tool (*www.randomizer.org*). This subject has a 1 in 3 chance of being assigned to any of the three treatment groups: "1" for Group 1 (LED-RL 160 J/cm²), "2" for Group 2 (LED-RL 320 J/cm²), or "3" for Group 3 (LED-RL 480 J/cm²). The next subject who enrolls is then similarly randomized to one of the remaining two treatment groups, and the following subject who enrolls is automatically assigned to the last treatment group. This block randomization process continues until each treatment group is filled with 10 subjects.

Split-Face Randomization

Within each treatment group, the treatment side (right face versus left face) will be determined using a computer-generated randomization tool (*www.randomizer.org*). The assignment to a treatment dose and a treatment side of the face occurs simultaneously. Within each treatment group, a single set of Arabic numerals "0" to "9" will be generated, resulting in a random sequence of 10 numerals for sampling without replacement. As subjects are allocated to a treatment group, they are assigned to a numeral in this set based upon their order of enrollment. In other words, the first subject to enroll in a treatment group is assigned to the first random numeral, the second subject to the second random numeral, etc. Subjects assigned to even numerals will receive LED-RL phototherapy on the right side of the face, making the left face the control. Subjects assigned to odd numerals will receive LED-RL phototherapy on the left side of the face, making the right face the control. Within each treatment group (n=10), 5 subjects will receive treatment on the right face and the other 5 subjects will receive treatment on the left face.

Blinding

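### Section 9.4.4 does not specify side of face for local adverse events in a split-face trial, and no part of Section 9 tabulates safety by skin type

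*Combined protocol and SAP*

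**What the plan says.** Section 9.4.4 gives the safety summary as the "number of subjects who experienced AEs in each treatment group and a breakdown of the event types", together with AEs leading to discontinuation and serious treatment-emergent AEs. It names neither side of face nor skin type.

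Treatment group means dose. Section 6.1.2 uses an algorithm to "assign subjects to three different treatment groups to receive LED-RL at the following doses", and Section 6.3 adds a second allocation inside each dose group: "Within each treatment group, the treatment side (right face versus left face) will be determined".

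The synopsis (Section 1.1) lists "Incidence of adverse events" among the secondary outcome measures. Section 9.4.3 states: "Secondary outcomes will be presented as descriptives tabulated by whether treated, treatment group and time, showing medians and ranges". So one section could imply a split of AEs by side, while the dedicated safety section does not mention one.

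On skin type, Section 3 promises special attention to differential safety findings. Section 4.1 defines two classes for that purpose: Caucasian non-Hispanic, and everyone else as skin of color. Sections 4.3 and 10.2 give further safety evaluation as a reason for allowing any skin type into the 480 J/cm² group. Section 2.3.1 allows that "subjects with darker skin types may experience a greater sensation of epidermal warmth, textural changes, or dyspigmentation".

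**The concern.** The split-face design gives each subject a concurrent randomised control for local events. That control matters because both sides have been operated on. Section 2.3.1 lists for the surgery effects such as "swelling, pain, skin sensitivity, skin contour irregularities, skin discoloration". For LED it lists swelling, tenderness, dyspigmentation and worsening of the surgical scar. A swollen or discolored incision in week two could come from either source, and comparing the two sides is the most direct way to tell them apart.

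If the AE table is built from 9.4.4 alone, a subject counts once whichever side is affected, and the comparison between sides does not appear. At stake is how the safety results can be read, dose by dose, in the first use of this treatment on surgical wounds. The skin-type gap is of another kind: the documents state an aim, and the analysis section contains nothing that delivers it.

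**Working it through.** The plan gives no figure on this point to reproduce. The check is a reading of the text followed by illustrations with assumed rates.

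**1. Side of face, section by section**
- 9.4.2 (primary) has treated versus not treated as a fixed factor.
- 9.4.3 (secondary) tabulates by treated status, dose group and time, as medians and ranges.
- 9.4.4 (safety) has the subject as its unit and dose group and event type as its groupings.
- 9.4.8 lists individual data by measure and time point.
- 8.3.4, 8.3.5 and 9.4.4 list the AE items recorded. These include relationship to the intervention. Side is not named.

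Safety is therefore the one outcome domain whose dedicated section leaves side out. Applying 9.4.3 to AEs would restore the split, but a median and range do not summarise how many subjects had an event.

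**2. What a per-subject count cannot show**

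Assume one dose group of 10 (Section 9.2) in which six subjects have a local event on one side only. Difference = (LED-only − mock-only)/10.

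| LED only | Mock only | Shown under 9.4.4 | Difference between sides |
|---|---|---|---|
| 6 | 0 | 6 of 10 | +60 points |
| 5 | 1 | 6 of 10 | +40 points |
| 4 | 2 | 6 of 10 | +20 points |
| 3 | 3 | 6 of 10 | 0 |
| 0 | 6 | 6 of 10 | −60 points |

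**3. When this matters little**

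If the sides are independent, the per-subject rate is 1 − (1 − pL)(1 − pM), where pL and pM are the LED-side and mock-side rates. With pL assumed to be 40%:
- pM = 0%: 1 − 0.6 × 1.0 = 40%
- pM = 10%: 1 − 0.6 × 0.9 = 46%
- pM = 20%: 1 − 0.6 × 0.8 = 52%

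With mock events near zero, the per-subject rate is close to the LED rate. The ambiguity remains when the mock rate is unknown. A per-subject rate of 40% also arises with no LED effect at all, from an equal rate on each side of 1 − √0.6 = 22.5%.

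**4. Skin type, section by section**
- 9.4.4: no breakdown by skin type.
- 9.4.5: race and ethnicity as baseline characteristics only.
- 9.4.7: race and ethnicity in a regression on pliability, an efficacy measure.
- 9.4.8: listings not specified by skin type.
- 9.4.9: not applicable.

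The documents do not say how many skin-of-color subjects the 480 J/cm² group will hold. Assume 3, 5 or 7 of the 10. With zero events in n subjects, the upper end of the exact two-sided 95% interval is 1 − 0.025^(1/n):
- n = 3: 71%
- n = 5: 52%
- n = 7: 41%

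Such a table can describe events but cannot establish or exclude a difference.

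**The case against.** The strongest reply is that 9.4.3 and 9.4.4 can be read together. AE incidence is a secondary outcome, and secondary outcomes are tabulated by treated status, so a by-side split may be intended. This stands in part. A reader might infer from 9.4.4 that the two sides are definitely pooled, but the documents do not establish that. What they show is a safety section silent on side, and a general rule whose summary statistics do not fit incidence.

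A reader might also infer that a stated side-against-side safety objective is being abandoned. The documents do not support this either. The efficacy endpoints are worded as differences between treated and control sites, while the safety endpoint is worded only as incidence.

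Relationship to the intervention is graded for every AE, which is a partial substitute. It is a clinician's judgement (Section 8.3.3.2), not a randomised comparison. The research coordinator who gives and observes treatment knows the codes (Sections 6.1.2 and 6.3), and 9.4.4 promises no table by relatedness.

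Section 2.3.1 reports that "there were no adverse events associated with the mock treatment device in the Phase I studies". That is a fair reason to expect few mock-side events. But Phase I treated normal skin, mock sides here carry incisions, and Section 4.2 itself says safety in a surgical wound may differ.

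Sections 8.2 and 8.3.1 speak of expected effects at the treated sites, so a reader might infer that mock-side effects go unrecorded. That is speculative. Section 8.2 has the periauricular skin examined at each visit, Section 8.3.4 requires all AEs to be documented whatever their relationship, and the case report form is not in the documents.

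Finally, with 30 subjects and race and ethnicity recorded, a skin-type breakdown could be produced later. That is true, and it lowers the urgency. Planning it now ties the table to the stated aim before the results are seen.

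**Conclusion.** The point holds at modest priority. The safety section does not specify side of face, 9.4.3 and 9.4.4 need reconciling for AE incidence, and the stated aim on safety by skin type has no matching analysis in Section 9.

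The size depends on the mock-side event rate, which the documents do not give for operated skin. All side rates and counts used in the check are assumptions. If mock-side events are near zero, little is lost. If they are appreciable, a per-subject count cannot separate an LED effect from none. The skin-type table would be descriptive only. The primary analysis is unaffected.

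**What to change.** In Section 9.4.4:

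1. State that AE incidence is reported as counts and proportions, and that for AEs this replaces the medians and ranges of 9.4.3.
2. Within each dose group, tabulate local AEs as subjects affected on the LED side only, the mock side only, or both. Do the same in a separate table for the recorded transient expected effects (erythema, warmth, edema). Keep systemic AEs per subject.
3. Confirm that side of face is captured for each local event.
4. Add a descriptive table or listing of LED-side local AEs, with blistering shown separately, by dose group and the Section 4.1 skin-type class. State that no inference will be drawn.

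The cost is a few sentences and a little more table work, with no extra patients or visits. There are limits. Skin-type cells will be very small, so zero events in five subjects still leaves an upper limit of 52%. In-session events are assessed by staff who know the treated side, so the by-side table is not observer-blind; flagging events from the blinded subjects' diaries would help. The gain is small if mock-side events turn out to be rare.
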